### **11.1 Demographics and Baseline Characteristics**

#### **Demographics:**

Ethnicity, race, sex, date of birth, height, body weight, inpatient/outpatient status at informed consent, and duration of hospitalization at informed consent

#### **Disease information:**

Time of the first onset of schizophrenia, the number of previous episodes of schizophrenia, time of onset of the current episode, and complications

### **11.2 Efficacy Assessments**

The concomitant use of medications is restricted, as described in Section 10.3 Concomitant Medications and Therapies (p38). When the efficacy assessments are conducted, the concomitant use of restricted medications will be recorded in the CRFs.

### **11.2.1 Positive and Negative Syndrome Scale (PANSS)**

The PANSSref.11 is an interview-based measure of the severity of psychopathology in adults with psychotic disorders.

A person, who will be a certified rater for PANSS assessments, will receive specific training and education for the PANSS assessment provided by the Sponsor/CRO and will be certified by the Sponsor/CRO before his/her initial assessment of PANSS. The certified rater will rate 30 items on a 7-point scale of 1 to 7. Dates of the assessments and the results will be recorded in the CRFs.

When the study treatment is completed or prematurely discontinued, PANSS will be rated before the first post-treatment with other antipsychotics. When the DSP-5423P dose is changed at an unscheduled visit in the open-label treatment phase, PANSS will be rated before dose adjustment.

### **11.2.2 Clinical Global Impressions scale-Severity of illness (CGI-S)**

CGI-Sref.12 is a research rating tool of the subject's current disease state on a 7-point scale of 1 to 7. The Investigators will receive specific training before their initial assessment of CGI-S. Dates of the assessments and the results will be recorded in the CRFs.

When the study treatment is completed or prematurely discontinued, CGI-S will be rated before the first post-treatment with other antipsychotics. When the DSP-5423P dose is changed at an unscheduled visit in the open-label treatment phase, CGI-S will be rated before dose adjustment.

## **11.3 Safety Assessments**

### **11.3.1 Adverse Events**

Adverse events will be collected for each subject. Subjects should be queried in a non-leading manner, without specific prompting (eg, "Has there been any change in your health status since your last visit?"). See Section 12 SAFETY REPORTING (p52).

AEs and SAEs will be monitored throughout the study at all visits including telephone assessments.

### **11.3.2 Drug Induced Extra-Pyramidal Symptoms Scale (DIEPSS)**

The DIEPSSref.13 is a rating tool of extrapyramidal symptoms induced by

antipsychotics and consists of 8 individual items; gait, bradykinesia, sialorrhea, muscle rigidity, tremor, akathisia, dystonia, and dyskinesia; and one global assessment; overall severity. The severity of each item is on a 5-point scale of 0 to 4. Dates of the assessments and the results will be recorded in the CRFs.

If the DSP-5423P dose is reduced due to extrapyramidal symptoms at an unscheduled visit in the open-label treatment phase, DIEPSS will be assessed before dose reduction.

### 11.3.3 Columbia-Suicide Severity Rating Scale (C-SSRS)

The C-SSRSref.14 is a rating tool designed to systematically assess and track suicidal behavior and suicidal ideation throughout the study. The C-SSRS can comprehensively identify suicidal events and limit the over-identification of suicidal behavior.

The Investigators will receive specific training before their initial assessment of C-SSRS. Date of the assessments and the results will be recorded in the CRFs.

### 11.3.4 Skin Irritation Assessment

The Investigator will evaluate any skin reactions at the application sites according to the Table 14 and record the score in the CRFs. If more than one skin reaction from + – to ++++ is observed at the application sites, the stronger reaction will be scored and recorded in the CRFs.

**Table 14 Scoring of Skin Reactionsref.15**

Skin reactions	Score
Negative	–
Faint erythema	+ –
Erythema	+
Erythema + Edema	++
Erythema + Edema + Papules, Serous papules, Vesicles	+++
Coalescing vesicles	++++

### 11.3.5 Clinical Laboratory Tests

Blood and urine samples will be collected for clinical laboratory tests. The Investigators will record the date of collection and whether or not the subject is under

fasting conditions (at least 10 hours after the last meal) in the CRFs. All clinical laboratory tests will be performed centrally.

The clinical laboratory tests required by the protocol are listed in Table 15. Detailed instructions regarding clinical laboratory procedures, sampling, shipping, and reporting can refer to the instructions manual provided by the Sponsor/CRO.

### Guidance for Blood sample Collection

- From screening until the end of the double-blind treatment phase  
Blood samples will be collected under fasting conditions (at least 10 hours after the last meal).
- During the open-label treatment phase  
Blood samples will be collected under fasting conditions (at least 10 hours after the last meal) at the last visit (Visit 109 outside Japan or Visit 112 in Japan). At other visits, blood samples should be collected under fasting conditions, whenever possible.
- At the discontinuation visit  
Blood samples will be collected under fasting conditions (at least 10 hours after the last meal).

**Table 15 Contents of laboratory variables**

Hematology	white blood cell count, red blood cell count, hemoglobin, hematocrit, platelet count, differential white blood cell count (neutrophils, eosinophils, basophils, monocytes, and lymphocytes)
Blood biochemistry	total protein, total bilirubin, AST, ALT, ALP, $\gamma$ -GTP, LDH, total cholesterol, triglycerides, BUN, creatinine, CK, Na, K, Cl, blood glucose, HbA1c, serum prolactin*
Urinalysis (Qualitative)	glucose, protein, occult blood, urobilinogen
Pregnancy test (premenopausal women of childbearing potential only)	urine chorionic gonadotropin

\* Serum prolactin concentrations measured from screening until the end of the double-blind treatment phase will not be disclosed until the other data of the double-blind treatment phase have been locked.

### 11.3.6 Vital Signs and Body Weight

Systolic and diastolic blood pressures (sitting), pulse rate, body temperature (axilla), and body weight will be measured. Dates of measurements and the results will be

recorded in the CRFs.

### **11.3.7 12-lead ECGs**

The Investigator will perform 12-lead ECG at rest and record the dates and times of assessments in the CRFs. The Investigator will retain ECG tracings and send them electronically to the central ECG reader. The central ECG reader will analyze ECG tracings and calculate the following ECG parameters: RR interval, QT interval, PR interval, QRS interval, and QTc interval (QTc Fridericia [QTcF] and QTc Bazett [QTcB]). The central ECG reader will report analysis results and ECG parameters to the Sponsor and the Investigator.

The principal ECG analyst will comprehensively evaluate the effect of study treatment on QTc prolongation.

## **11.4 Pharmacokinetic Assessments**

### **Measurement**

- Plasma concentrations of blonanserin
- Plasma concentrations of M-1 (N-de-ethylated metabolite)

### **Recording**

The following information will be recorded in the CRFs:

- Dates and times of blood sample collection
- Dates and times of the last two applications of DSP-5423P before blood sample collection
- Locations for the last two applications of DSP-5423P before blood sample collection
- DSP-5423P doses of the last two applications before blood sample collection (in the open-label treatment phase only)

### **Timing and volume of blood collection**

Six milliliters of blood will be collected at each time point shown in Table 3 to 5 Schedule of Assessments.

### **Processing of blood collection**

Blood samples will be collected into heparinized (heparin sodium) blood collection tubes and should be stored in ice before being centrifuged (4°C, 3000 rpm [approximately 1700 g], 10 minutes). The entire volume of plasma will be placed in a container and stored in a freezer (set at -20°C or lower).

When a centrifuge with cooling system is not available, ice chilled blood samples should be centrifuged (at room temperature, 3000 rpm [approximately 1700 g], 10 minutes) as immediately as possible. The entire volume of plasma should be also placed in a container as immediately as possible and will be stored in a freezer (set at  $-20^{\circ}\text{C}$  or lower).

### **Shipment of specimens**

All specimens for drug concentration measurements will be collected by the clinical laboratory and shipped to the bioanalysis laboratory.

### **Measurements and Reporting**

The bioanalysis laboratory will measure the plasma concentrations of blonanserin and its metabolite M-1 and prepare a bioanalysis report. Results obtained in the double-blind treatment phase will be reported to the Sponsor after unblinding.

## **12. SAFETY REPORTING**

### **12.1 Definitions**

#### **12.1.1 Adverse Events**

An adverse event (AE) is any untoward medical occurrence in a study subject administered a medicinal (investigational) product and which does not necessarily have a causal relationship with this treatment. An AE can, therefore, be any unfavorable and unintended sign (including an abnormal laboratory finding), symptom, or disease occurring after the administration of a medicinal (investigational) product, whether or not considered related to the medicinal (investigational) product. AEs may include the onset of new illness and the exacerbation of pre-existing conditions. AEs will be collected from the beginning of the study treatment in the washout phase until the follow-up visit. AEs also include other untoward events occurring from the beginning of the study treatment in the washout phase until the follow-up visit, for instance, events occurring in association with study-related procedures or assessments, or those occurring under placebo treatment.

AEs that occur during the washout phase and worsen during the double-blind treatment phase will be recorded as AEs in the washout phase and also as AEs in the double-blind treatment phase. AEs that occur during the washout phase and worsen during the open-label treatment phase will be recorded as AEs in the washout phase and also as AEs in the open-label treatment phase. The date of worsening will be

recorded as the onset date of the worsening AE. Likewise, AEs that occur during the double-blind treatment phase and worsen during the open-label treatment phase will be recorded as AEs in the double-blind treatment phase and also as AEs in the open-label treatment phase, with the date of worsening as the onset date. In addition, AEs that occur during the washout phase or double-blind treatment phase without further worsening in the following phase will be recorded as AEs in the washout phase or as AEs in the double-blind treatment phase, respectively.

Lack of efficacy may be an expected potential outcome and should not be reported as an AE unless the event is unusual in some way. New signs and symptoms of the underlying disease, or signs and symptoms of an emerging disease should be recorded as AEs.

The Investigator should attempt to establish a diagnosis of the event based on signs, symptoms, and/or other clinical information. In such cases, the diagnosis should be recorded as the AE and not the individual signs/symptoms.

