### 10.3.1 Antipsychotics

Antipsychotics except for the study drug will be restricted as follows:

- For the subjects not treated with antipsychotics at screening  
Antipsychotics will be prohibited from screening until completion of assessments at the last visit (Visit 109 outside Japan or Visit 112 in Japan) of the open-label treatment phase or the discontinuation visit. If a subject completes the double-blind treatment phase and discontinues before entering the open-label treatment phase, antipsychotics will be prohibited until completion of assessments at Visit 6.
- For the subjects treated with any antipsychotics at screening  
The antipsychotics should be tapered and completely discontinued before the beginning of the washout phase. Antipsychotics will be prohibited from the beginning of the washout phase until completion of assessments at the last visit (Visit 109 outside Japan or Visit 112 in Japan) of the open-label treatment phase or the discontinuation visit. If a subject completes the double-blind treatment phase and discontinues before entering the open-label treatment phase, antipsychotics will be prohibited until completion of assessments at Visit 6.

If urgent treatment is required because of psychiatric symptoms such as acute psychomotor excitability during the open-label treatment phase, at the discretion of the Investigator, only one antipsychotic drug excluding depot neuroleptics and blonanserin can be used concomitantly on an as-needed basis. However, all antipsychotics will be prohibited within 48 hours before the PANSS, CGI-S, and C-SSRS assessments. The total duration of concomitant use of antipsychotics for urgent treatment during the open-label treatment phase should be 5 days or less outside Japan, and 10 days or less in Japan.

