### **10.3.2 Antimanic and Antiepileptic drugs**

Antimanic and antiepileptic drugs will be prohibited from screening until completion of assessments at the last visit (Visit 109 outside Japan or Visit 112 in Japan) of the open-label treatment phase or the discontinuation visit. If a subject completes the double-blind treatment phase and discontinues before entering the open-label treatment phase, antimanic and antiepileptic drugs will be prohibited until completion of assessments at Visit 6. When psychiatric symptoms worsen during the open-label treatment phase, antimanic and antiepileptic drugs may be used. If the psychiatric symptoms improve, antimanic and antiepileptic drugs may be tapered or discontinued.

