#### **(1) From screening until the end of the double-blind treatment phase**

- For the subjects not treated with antiparkinson drugs at screening  
Antiparkinson drugs will be prohibited from screening until completion of DIEPSS assessments at Visit 6 or the discontinuation visit.
- For the subjects treated with antiparkinson drugs at screening  
Antiparkinson drugs will be tapered and completely discontinued before beginning of the washout phase. Antiparkinson drugs will be prohibited from the beginning of the washout phase until completion of DIEPSS assessments at Visit 6 or the discontinuation visit.

If extrapyramidal symptoms occur or worsen during the washout phase or double-blind treatment phase, only one of the antiparkinson drugs listed in Table 11 may be used and the dose may not exceed the maximum daily dose. If the antiparkinson drug is not effective, the drug may be switched to another antiparkinson drug listed in Table 11. If the drugs listed in Table 11 are not available outside Japan, another similar drug at an equivalent dose will be permitted with prior authorization of the medical monitor (Table 1 Emergency Contact Information for outside Japan, p3). If the extrapyramidal symptoms improve, antiparkinson drugs may be tapered or discontinued.

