**(1) From screening until the end of the double-blind treatment phase**

Psychotropics will be prohibited from screening until completion of assessments at Visit 6 or the discontinuation visit.

When psychiatric symptoms, such as anxiety, agitation and irritation, occur, lorazepam may be used as needed at 3 mg/day or less. If lorazepam is not available outside Japan, another similar drug at an equivalent dose may be used with prior authorization of the medical monitor (Table 1 Emergency Contact Information for outside Japan, p3).

However, all psychotropics will be prohibited within 12 hours before assessments of the PANSS, CGI-S, and C-SSRS.

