## **12.3 Collection and Recording Adverse Events**

All AEs will be, in principle, followed up until resolution, stabilization of the condition, the event is otherwise explained, or the subject is lost to follow-up. All AEs must be collected and recorded in the subject's study records/source documents, in accordance with the Investigator's normal clinical practice. AEs will be recorded in the CRFs

from the beginning of the study treatment in the washout phase until the follow-up visit.

Each AE is to be evaluated for duration, severity, seriousness, action taken with the study treatment, outcome, and causal relationship to the study treatment. If any AEs related to skin disorders occur at the application site, the Investigator will record the location (the back, chest or abdomen) of AEs occurrence.

Definitions for severity, action taken with the study treatment, outcome, and causal relationship to the study treatment are presented below.

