**12.4.1 Serious Adverse Event**

If the Investigator or staff of study centers becomes aware of SAE that occurs in a

study subject from the beginning of the study treatment in the washout phase until the follow-up visit, this must be reported immediately to the Sponsor/CRO whether considered related or unrelated to the study drug. SAEs occurring from the beginning of the study treatment in the washout phase until the follow-up visit must be recorded in the CRFs.

Following the end of subject participation in the study, the Investigator should report SAEs “spontaneously” to the Sponsor/CRO if considered at least possibly related to the study drug.

SAEs will be followed until resolution, loss to follow-up, stabilization of condition, or the event is otherwise explained.

The Investigator must inform the Sponsor/CRO (Table 1 and 2 Emergency Contact Information) of any SAEs that occur during the course of the study within 24 hours of the Investigator becoming aware of the SAE.

The SAE report should include the following information:

1. Study number (D4904020)
2. Subject number
3. Sex
4. Date of birth
5. Name of investigator and study site
6. Nature of SAE
7. Criterion for classification as “serious”
8. Date of initial administration of the study drug
9. Start date of SAE
10. Causality (if sufficient information is available to make this classification)
11. History of any ADRs
12. Relevant special conditions of the subject
13. History of the current disease and treatment for the disease
14. Details of the SAE
15. Treatment for the SAE
16. Details of study treatments
17. Details of concomitant medications
18. Details on course of the SAE
19. If the subject died, date of death, cause of death, relationship between the SAE

and death, anatomic findings (if available)

As a minimum requirement for the first report, information on items 1 to 10 described above should be provided directly or in a form of a report, by facsimile, or by telephone. The Principal Investigator should report available information in writing within 7 calendar days after the first reporting (this procedure is not mandatory in the case that the Principal Investigator has already submitted the first report, including all necessary information listed above). The Principal Investigator should report other necessary information not included in the first and second reports in writing as it becomes available. The Sponsor/CRO may request additional information, if deemed necessary.

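### AE and SAE collection starts at the first washout patch, by which time antipsychotics and antiparkinson drugs must already be stopped, so 0 to 18 days of required withdrawal fall outside the stated window

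*Protocol*

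**What the plan says.** Three protocol sections set the start of collection. Section 12.1.1: "AEs will be collected from the beginning of the study treatment in the washout phase until the follow-up visit". Section 12.3 has AEs entered in the CRF "from the beginning of the study treatment in the washout phase until the follow-up visit". Section 12.4.1: "SAEs occurring from the beginning of the study treatment in the washout phase until the follow-up visit must be recorded in the CRFs". Pregnancy reporting in 12.4.2 starts at the same point.

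The medication rules act earlier. For subjects on antipsychotics at screening, 10.3.1 says: "The antipsychotics should be tapered and completely discontinued before the beginning of the washout phase". Section 10.3.5.1 is parallel: "Antiparkinson drugs will be tapered and completely discontinued before beginning of the washout phase". Other classes are barred from screening itself. Section 10.3.2: "Antimanic and antiepileptic drugs will be prohibited from screening until completion of assessments at the last visit". Section 10.3.5.2: "Psychotropics will be prohibited from screening until completion of assessments at Visit 6 or the discontinuation visit". Hypnotics are treated similarly in 10.3.5.3. Limited use of lorazepam and of listed hypnotics remains possible.

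Section 12.1.1 does not confine AEs to active drug. It also counts "events occurring in association with study-related procedures or assessments, or those occurring under placebo treatment".

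**The concern.** Stopping antipsychotic and antiparkinson treatment is a step the protocol imposes on a consented patient, and it has to be finished before the AE clock starts. These are inpatients with an exacerbation in the previous 60 days and a PANSS total of at least 80 (Protocol 8.1.1). If such a patient relapses seriously or attempts suicide while drugs are being withdrawn, the three collection rules do not count the event.

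At stake is the sponsor's view of a risk created by the entry procedure, and consistent reporting across sites. The efficacy analysis is not involved.

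**Working it through.** The plan states no figure for this interval, so there is nothing to reproduce. The check is day arithmetic followed by a comparison of the rules.

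**Inputs.** From Protocol Table 3: screening (Visit 1) on Day -21 to -4, and start of washout on Day -7 to -3. From 10.1.1: washout lasts one week in principle and at least 3 days.

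**Formula.** Gap = day of first washout patch minus day of screening. Both days are negative, so the absence of a Day 0 does not matter.

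| Screening | First patch | Gap (days) |
|---|---|---|
| Day -21 | Day -3 (3-day washout) | -3 - (-21) = 18 |
| Day -21 | Day -7 (one-week washout) | -7 - (-21) = 14 |
| Day -14 | Day -3 | -3 - (-14) = 11 |
| Day -7 | Day -3 | -3 - (-7) = 4 |
| Day -4 | Day -3 | -3 - (-4) = 1 |
| Day -7 | Day -7 | -7 - (-7) = 0 |

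The two windows overlap from Day -7 to Day -4, so the minimum is 0. The maximum of 18 needs the earliest screening together with the shortest washout. Table 3 puts consent before screening without a window, so any time between consent and Visit 1 comes on top.

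**What the stated window captures.**

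- Event starts and resolves before the first patch: not captured.
- Event starts before the first patch and persists unchanged: not captured.
- Event leads to dropout before the first patch: not captured. The discontinuation assessments in 13.2 apply to subjects who have applied study drug in washout, or who are randomized.
- Event starts before the first patch and worsens afterwards: recordable, because 12.1.1 counts exacerbation of pre-existing conditions.
- Event starts after the first patch: captured.

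**Other records in the interval.** Section 10.3 has medications recorded from screening with start date, stop date and reason, so the CRF shows the drug being stopped. C-SSRS and DIEPSS are first rated at Visit 2 (Table 3), after the withdrawal. SAP 7.2 tabulates subjects not entering washout by reason, which is disposition and not event reporting.

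**Sentences that point to an earlier start.** Section 11.3.1 has AEs and SAEs monitored at every visit over the whole study. Section 12.1.2, on hospitalizations planned beforehand, equates study entry with informed consent and makes worsening of a pre-study condition during the study reportable. Section 12.4.1 also requires 24-hour notice of any SAE in the course of the study. None of these gives a start date that overrides the washout start. A site applying 12.1.2 could report a relapse during the taper; a site applying 12.1.1, 12.3 and the recording rule in 12.4.1 could leave it out.

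**The case against.** A fair defence has four parts.

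1. No study product has been applied before the first patch, so starting there is a recognizable choice. This has some force, but 12.1.1 already takes in events tied to study procedures and events under placebo. A study-required withdrawal fits that logic and is left out only by the start date.

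2. The protocol contains broader sentences (11.3.1, 12.1.2, 12.4.1), and the duty in 17.2 to inform the IRB/IEC of SAEs sets no washout start. This stands. A reader might infer that no withdrawal event would ever reach the sponsor; the documents do not support that. They show a conflict that sites could resolve either way.

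3. The withdrawal is narrower than it may look. A reader might infer that all psychotropic drugs are tapered in the interval. Only antipsychotics and antiparkinson drugs have a prescribed taper there. Antimanic and antiepileptic drugs, other psychotropics and hypnotics are barred from screening with no taper described. An argument built on seizures after stopping an antiepileptic would therefore rest on a step the protocol does not set out.

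4. Timing is partly recoverable. PANSS, CGI-S, laboratory tests, ECG and vital signs are taken at both screening and Visit 2, and medication dates are kept. This also stands, so it would be too strong to say that withdrawal events cannot be told apart from later ones. These records are still not AE or SAE reports, and a subject who leaves before Visit 2 does not have the second set.

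**Conclusion.** The point holds as a gap in the stated collection window combined with an internal conflict. The gap is 0 to 18 days from screening, and at most 14 with the nominal washout. What is lost is events that resolve, persist unchanged or cause dropout before the first patch.

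Its size in subjects is unknown. One might be tempted to scale it by the 582 randomized in SAP Appendix II, but that number does not count the affected. Section 10.3.1 has a separate branch for subjects on no antipsychotic at screening, the split is not given, and subjects who never reached randomization are not in it. Event rates are not given either.

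Nor does the gap bias the treatment comparison. Treatment-emergent AEs begin on Day 1 (Protocol 15.3.6.1; SAP 7.7.1), after the whole interval.

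Two items could not be checked: the AE-monitoring arrow in Table 3, which is missing from the available text, and the Japan Appendix, which was not supplied. Either might already set an earlier start. On the text available, this is an inexpensive improvement to safety reporting and leaves the trial's main conclusion untouched.

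**What to change.** State in 12.1.1, 12.3 and 12.4.1 that SAEs, and AEs the Investigator attributes to a study-required medication change, are collected and reported from informed consent. Label them pre-washout and list them for all consented subjects, including those never randomized. Align 11.3.1, 12.1.2 and the 24-hour sentence in 12.4.1 with that start, and check Table 3 and the Japan Appendix for consistency. The medication rules themselves need no change for this purpose.

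The treatment-emergent definitions and every treatment-comparison table stay as they are. No visit is added, because subjects are hospitalized from screening (10.4). The cost is some additional SAE reports, including from screen failures, one listing, and CRF fields for the phase and for attribution to the medication change. The attribution field is needed because 12.3 rates causality only against study treatment.
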